## **15.6 Study Population Summary**

The ITT analysis set will be used to describe study population. Descriptive statistics of these data will be provided by treatment group and overall.

### **15.6.1 Subject Disposition**

Data from subjects who are randomized, subjects who are randomized regardless of treatment (ITT), mITT, CO, PP and ST analysis sets, subjects who have reached the End of Study visit according to study plan, subjects who early discontinued treatment or study follow-up will be summarized. Data from subjects who early discontinued study IP treatment or study follow-up will also be displayed by discontinuation reason using descriptive statistics. The denominator for calculating the percentages will be the set of ITT. This summary table will also describe all subjects screened into the study.

### **15.6.2 Study Inclusion and Exclusion Criteria**

Although it is expected that all subjects randomized into the study will meet all study inclusion and exclusion criteria there might be some subjects that will be granted waivers allowing them to be enrolled into the study. The number and proportion (%) of the ITT analysis set subjects who failed to meet study inclusions/exclusion criteria will be reported broken down by criteria.

### **15.6.3 Demographics and Baseline Characteristics**

Demographics and baseline data will be displayed for the ITT analysis set. Subject demographic and baseline characteristics, including baseline prognostic factors will be examined to assess the comparability of the treatment groups. For continuous variables, descriptive statistics (number [n], mean, standard deviation (SD), standard error, median, minimum, and maximum) will be provided. For categorical variables, subject counts and percentages will be provided. Categories for missing data will be presented.

Summary statistics of these parameters will also be provided when broken down by geographical region, and by US/Non-US sub-populations.

### **15.6.4 Medical History**

The incidence (no. of patients) of past medical conditions will be provided when broken down by System Organ Class (SOC) and Preferred Term (PT) according to MedDRA dictionary. Subjects

with at least 1 past medical condition in each SOC/PT category will be summarized using descriptive statistics. Subjects will be counted only once in each category.

### **15.6.5 Prior and Concomitant Medications**

All prior and concomitant medications will be coded using the WHODRUG dictionary. The incidence of prior medications and separately those consumed concomitantly; from the day of 1st study IP administration and onwards, will be summarized using descriptive statistics by Therapeutic Main Group (ATC Level 2) and dictionary Preferred Term.

Subjects will only be counted once in each Therapeutic Main Group, and only once in each Preferred Term category.

#### ***15.6.5.1 Pre-Study Medications***

Analyses will include only coded medications that were initiated one day or more prior to the 1st administration of study IP. Medications in which start date will not be reported in the database will also be considered as pre-study medications.

Incidence table including subject counts (no. of subjects) and percentages broken down by Therapeutic Main Group and Preferred Term as well as by treatment group will be generated.

Summary statistics of pre-study medications will also be provided when broken down by US/Non-US sub-populations.

#### ***15.6.5.2 Concomitant Medications***

Analyses will include only coded medications that were consumed after 1st study IP administration. Medications in which start date will not be reported in database will also be considered as concomitant medications. Medications lacking stop date will be considered as ongoing for the purpose of analysis.

Incidence table including subject counts (no. of subjects) and percentages broken down by Therapeutic Main Group and Preferred Term as well as by treatment group will be generated.

Summary statistics of concomitant medications will also be provided when broken down by US/Non-US sub-populations.

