### **8.3.5 Concomitant Medications**

Concomitant medication logs will be completed at the Screening visit and will be updated at each subsequent visit. The logs will include the medication taken by the subject over the past 3 months. A separate log will record anti-PD medications that were previously used.

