## **13 SAFETY/ADVERSE EVENTS**

### **13.1 Adverse Events definition**

An adverse event is any untoward medical occurrence in a clinical investigation subject who is administered a medicinal product whether or not considered related to the medicinal product. An AE can therefore be any unfavorable and unintended sign (including an abnormal laboratory finding, for example), symptom or disease (new or exacerbated), temporally associated with the

use of a medicinal product, whether or not considered related to the product. Pre-existing signs and symptoms should not be considered AEs unless they worsen unexpectedly post-study drug administration. In addition, any study procedure-related AE that occurs after study participants have signed the Informed Consent Form (ICF) and prior to administration of the first dose of study drug will be recorded as an AE. Any adverse event that occurs post-study drug administration will be considered a treatment-emergent AE. Any adverse event that occurs prior-study drug administration will be considered a baseline-emergent AE. Again, all events should be entered whether or not the event is considered to be related to the study drug.

The date of onset, a description of the AE, severity, seriousness, action taken, relationship to the study drugs (causality), outcome of the event and date of resolution will be recorded. The final study report will include all of these details for each AE as well as the calculated duration.

The Investigator will assess the severity of the AE as:

- mild: AE which is easily tolerated
- moderate: AE sufficiently discomforting to interfere with daily activity.
- severe: AE which prevents normal daily activities.

The Investigator will assess the causality of the AE as (see section 13.2):

- unrelated
- possibly related
- probably related

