### 15.7.1 Adverse Events

Adverse events will be recorded from the time a subject has signed the Informed Consent Form until the end of subject's study participation, including up to Week 14 Follow-Up visit, regardless of study IP administration.

The MedDRA dictionary will be used to standardize the terms used by the Investigator to describe the Adverse Events (AEs).

The following will be incorporated into the analysis of adverse events:

- As analysis of AEs can incorporate only coded AEs, it is mandatory that at the time of database lock all AEs will be coded.
- Adverse events analyses will include only the Treatment Emergent Adverse Events (TEAEs), namely, those events which started at the time of first study IP administration or afterwards. AEs lacking start day or AEs recorded on day of first study IP lacking start time will be considered as TEAE.

The following analyses are pre-planned for adverse events:

- The incidence (no. of patients) and frequency (no. of events) of most frequent TEAEs (>5% of subjects in at least one study arm) by Preferred Term (PT).
- The incidence (no. of patients) and frequency (no. of events) of TEAEs broken down by System Organ Class (SOC) and PT.
- The incidence (no. of patients) and frequency (no. of events) of TEAEs by SOC and PT in Subjects Early Discontinued from Study/Treatment.
- The incidence (no. of patients) and frequency (no. of events) of serious TEAEs by SOC and PT
- The incidence (no. of patients) and frequency (no. of events) of TEAEs when broken down by severity.
- The incidence (no. of patients) and frequency (no. of events) of TEAEs broken down by relationship to study IP.
- The incidence (no. of patients) and frequency (no. of events) of TEAEs when broken down by action taken with study IP.
- The incidence (no. of patients) and frequency (no. of events) of TEAEs when broken down by event outcome.
- Adverse Events dictionary used to code Investigator's verbatim terms will be provided.
- Individual subject listings of all SAEs, treatment emergent SAEs, TEAEs and non-TEAEs.

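### The missing-start-date rules class medications as concomitant and adverse events as treatment-emergent, with no exception when a recorded stop or resolution date shows they ended before the first dose

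*Protocol*

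**What the plan says.** Protocol section 15.6.5 describes concomitant medications as those taken from the first dosing day on. Section 15.6.5.2 opens with a matching restriction, "Analyses will include only coded medications that were consumed after" first dosing. It then adds: "Medications in which start date will not be reported in database will also be considered as concomitant medications". Its one sentence on stop dates deals with a missing one: "Medications lacking stop date will be considered as ongoing for the purpose of analysis".

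Section 15.6.5.1 has a parallel rule for the other table: "Medications in which start date will not be reported in the database will also be considered as pre-study medications".

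For adverse events, section 15.7.1 restricts analysis to events that began at or after the first dose, and then states: "AEs lacking start day or AEs recorded on day of first study IP lacking start time will be considered as TEAE". Section 13.1 says of earlier events: "Any adverse event that occurs prior-study drug administration will be considered a baseline-emergent AE". The same section lists the fields to be collected and includes the end date: "outcome of the event and date of resolution will be recorded".

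The SAP addendum deals with the mITT set and the mapping of early termination visits. It contains no rule on medication or adverse event dates.

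**The concern.** Both rules look only at the start date. A record with an unknown start and a known end before dosing is not uncertain: it is pre-dose. As written, it is still reported as on-treatment.

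Such records can arise. On medications, section 8.3.5 says: "The logs will include the medication taken by the subject over the past 3 months". Drugs stopped before randomised treatment will therefore be in the data. Adverse events are collected from consent, so events that resolve during screening will be there too.

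Two kinds of output are at stake. The concomitant medication tables would list drugs that were not taken on treatment. The treatment-emergent tables would include events that treatment could not have caused, and those counts feed the exploratory adverse event comparisons with pramipexole ER in section 15.6.11. Section 15.6.10.5 allows exploratory endpoints to be tested at an unadjusted 5%.

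**Working it through.** The plan states no figure to reproduce, so the check is to apply the rules as written to each type of record and compare the result with the protocol's own definitions.

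| Record | Class under the stated rules | Class under the definitions |
|---|---|---|
| Medication, start missing, stop before first dose | Pre-study (15.6.5.1) and concomitant (15.6.5.2) | Pre-study only (15.6.5) |
| Medication, start missing, stop missing | Pre-study and concomitant | Unknown; the default is reasonable |
| Medication, start missing, stop after first dose | Pre-study and concomitant | Concomitant is right |
| Adverse event, start missing, resolved before first dose | Treatment-emergent (15.7.1) | Baseline-emergent (13.1) |
| Adverse event, only the day of onset missing, month of onset earlier than the month of first dose | Treatment-emergent, if a partial date counts as lacking a start day | Baseline-emergent (13.1) |
| Adverse event, start missing, resolution missing or after first dose | Treatment-emergent | Unknown; the default is reasonable |

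The first, fourth and fifth rows go wrong. In each, a date already on the record settles the class. The fifth depends on how the wording about a missing start day is read. The fourth is wrong under either reading.

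**Size for adverse events (assumptions, not document figures).** Let 5-10% of recorded events precede the first dose and 5-10% of those lack a start day, all of them provably pre-dose.

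- Lower end: 5% × 5% = 0.25% of recorded events.
- Upper end: 10% × 10% = 1% of recorded events.
- As a share s of events counted as treatment-emergent: 0.25 / (95 + 0.25) = 0.26%, and 1 / (90 + 1) = 1.1%.

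**Effect on the comparison of event rates.** Suppose false events add the same expected number per patient to each arm, and let s be their share in the pramipexole ER arm.

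- Rate difference: (a + c) − (b + c) = a − b, so it is unchanged in expectation.
- Rate ratio: observed ratio − 1 = (1 − s) × (true ratio − 1). The departure from 1 shrinks by the fraction s, about 0.26% to 1.1% here if s is similar in each arm.

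For a proportion of patients with at least one event, if a share q of patients in each arm has a false event independently of true ones, the difference is multiplied by (1 − q). That is again a slight shrinkage when q is small.

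**Size for medications.** The documents do not say how many pre-dose medications lack a start date. On an assumption of 10-30%, that share of medications stopped before the first dose would appear in the concomitant table as well as in the pre-study table.

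**The case against.** The strongest objection is that date handling belongs in the SAP. Sections 2 and 15.13 give the SAP precedence, and the addendum shows that Version 2.0 exists. Only the addendum is at hand, so the exception may already be there. This stands as a condition on the finding, but nothing in the available documents supplies the exception.

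Second, section 15.6.5.2 can be read coherently without the fault. Its opening sentence limits the table to drugs used after dosing, and the sentence on missing stop dates makes most sense if stop dates help decide that. On this reading, the missing-start sentence resolves only uncertainty about the start, and a known early stop still excludes the record. The reading is possible, but the text does not state it: the missing-start sentence adds undated records without a condition. Two programmers could reasonably code it differently.

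Third, counting unknown onset as treatment-emergent is the cautious choice for safety, and section 15.7.1 also provides listings of treatment-emergent and other events. Both points are right, and the default should stay for truly unknown timing.

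A reader might infer more than the documents support:

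- *That undated medications leave the pre-study table.* Section 15.6.5.1 keeps them there. They are counted twice, not moved.
- *That former anti-PD drugs will appear as co-treatment.* Sections 8.3.5 and 10 put these in a separate log, and nothing says that log feeds the concomitant table. An amantadine course of unknown start would also be hard to check against the duration limit in exclusion criterion 8.
- *That pre-dose events accumulate over 90 days.* The standard screening window is 28 days. Extension to 35 days needs sponsor approval, and extension up to 90 days also needs new laboratory samples.

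**Conclusion.** The point holds as a minor defect in the stated rules. For records whose own dates prove they ended before the first dose, section 15.6.5.2 conflicts with the definition in section 15.6.5, and section 15.7.1 conflicts with section 13.1 and with its own restriction to events starting at or after dosing.

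The number of affected records is not given; the percentages above are illustrations only. The reach is limited to the descriptive medication tables, the treatment-emergent tables and the exploratory adverse event comparisons with pramipexole ER. A reader might infer a material bias in those comparisons. The documents do not support that: the rules apply alike to all arms, so false events should be balanced in expectation and would only slightly attenuate ratios and proportions. The primary and key secondary analyses are unaffected.

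The conclusion applies to the protocol text and the SAP addendum, and rests on SAP Version 2.0 not already containing the exception.

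**What to change.** First check SAP Version 2.0. If it already lets a known stop or resolution date override the missing-start default, nothing more is needed.

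Otherwise, keep the default for truly unknown timing and add an exception to both rules:

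- *Medications:* an undated start counts as concomitant unless the recorded stop date is before the first dose. Such a record then appears only as pre-study.
- *Adverse events:* an event lacking a start day counts as treatment-emergent unless the recorded resolution date, or the known month and year of onset, shows that it resolved or began before the first dose. Such an event is then baseline-emergent.

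The second rule should also say whether a missing start day means that the whole date or only the day is absent.

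The cost is one clause in each rule and a matching line in the derivation programs. No new data are needed: section 13.1 already collects the resolution date, and section 15.6.5.2 presupposes medication stop dates.

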#### ***15.6.5.3 Disallowed Medications Use***

The following medications are disallowed:

- Other investigational therapy (washout period 30 days prior to study entry, baseline visit)
- Previous MAO-B inhibitors, selegiline or rasagiline, for longer than 4 weeks or within the previous 3 months prior to baseline visit.
- Previous levodopa or dopamine agonists, for longer than 4 weeks or within the previous 2 months prior to baseline visit.
- Previous anticholinergic drugs for PD (such as benzotropine, orphenadrine hydrochloride, biperiden, ethopropazine, procyclidine, trihexyphenidyl) or amantadine for longer than 4

weeks; if previous exposure was less than 4 weeks then it must not be within 1 month prior to the baseline visit.

- Subjects can take peripheral anticholinergic drugs (such as oxybutynin, orphenadrine citrate, tiotropium bromide etc..) if they are stable on low dose for at least 4 weeks prior to study entry, and without (or with minor) cognitive effects; however, once enrolled into the study use of new peripheral anticholinergic drugs is prohibited. Patients should be followed very closely for possible cognitive side effects.
- MAO inhibitors, such as phenelzine or tranylcypromine
- Dopamine antagonists, such as the neuroleptics (phenothiazines, butyrophenones, thioxanthenes) or metoclopramide.
- Ciprofloxacin or other CYP1A2 inhibitors: may affect rasagiline plasma concentrations.
- Antitussive agent Dextromethorphan.: co-administration with rasagiline may lead to psychosis.
- Analgesic agents such as tramadol, methadone, meperidine and propoxyphene due to risk of serotonin syndrome.
- St. John's Wort or cyclobenzaprine (tricyclic muscle relaxant).
- Marijuana or previous exposure to Marijuana during the last 30 days prior to the baseline visit.

Incidence table including subject counts (no. of subjects) and percentages broken down by treatment group will be generated and data listing will be provided.

#### **15.6.6 Protocol Violations/Deviations**

Protocol deviations and violations will be recorded on an ongoing basis and will be included in a DV domain in the SDTM database.

The number of subjects with at least 1 protocol violation/deviation in each category will be summarized using descriptive statistics. Detailed individual subject listing will also be provided.

#### **15.6.7 Efficacy Endpoints and Analyses**

All efficacy endpoints will be tested for the ITT analysis set controlling for multiplicity as detailed in Section 15.5.

An effort to obtain the efficacy outcome measures data regardless if study treatment was discontinued will be made.

Week 12/Treatment Termination is defined for all statistical analyses involving significance testing as the last visit in which a subject was treated with the study drug.

#### **15.6.8 Primary Efficacy Endpoint and Principal Statistical Analysis**

The primary efficacy endpoint for this study is the change from baseline to Week 12/Treatment Termination in total UPDRS score (defined as sum of parts II and III, scores (0-160). The statistical

model will be a Mixed Model for Repeated Measures (MMRM) (SAS® MIXED procedure with REPEATED sub-command). The model will include the following fixed effects: categorical week in trial by treatment interaction, country or geographical region (CGR), and baseline UPDRS score. The model will use the unstructured covariance structure and the REML estimation method and degrees of freedom will be adjusted using the Kenward-Roger method. Data from all three changes from baseline to post-baseline visits (weeks 4, 8 and 12) collected from all subjects randomized into the study will be used as response in the model. The differences between the P2B001 0.6/0.75mg arm as compared to its 2 individual components at Week 12/Treatment Termination will be estimated and tested using 2 contrasts: P2B001 0.6/0.75mg vs. pramipexole 0.6mg and P2B001 0.6/0.75mg vs. rasagiline 0.75mg. The study primary endpoint will be considered as met only if both contrasts will favor P2B001 0.6/0.75mg at a two-tailed alpha level of 5% each.

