### **8.4.1 UPDRS – see Appendix IX**

The UPDRS assesses motor and functional abilities of the subjects. The total UPDRS is defined for this study as the sum of Parts II and III (Activities of Daily Living and Motor sections). These will be completed by history and examination. UPDRS II and III will be performed at baseline visit and at end of weeks 5, 8 and 12/Treatment Termination (visits 4, 5, and 6). UPDRS part III will be completed also at screening visit to support diagnosis and the score will be included in the RAF.

The UPDRS part III evaluation will be conducted by a trained neurologist or other senior trained research staff with at least 10 years' experience in conducting the UPDRS. All attempts will be made to ensure that the same trained research staff member performs the UPDRS part III at all visits for each subject and at approximately the same time of the day and time following administration of medication. The UPDRS part II will be completed by a trained neurologist or other trained research staff member as delegated by the Site PI. For consistency efforts must be made to ensure that the same trained research staff member will do the UPDRS part II at all required visits for all subjects.

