## **15.1 Sample Size Rationale**

The study was powered to allow achieving two goals:

- To demonstrate the superiority of P2B001 0.6/0.75mg compared to its individual components in the primary endpoint, the change from baseline to Week 12/Treatment Termination in total UPDRS score:

- The power to meet the primary endpoint was estimated based on simulation runs assuming equal arms size of P2B001 0.6/0.75mg and its individual components as well as repeated UPDRS measurements at baseline, week 4, week 8 and week 12.
- The expected STD of the change from baseline was assumed to be 6.0 UPDRS points.
- The expected treatment effect of P2B001 0.6/0.75mg is 3 UPDRS points over rasagiline 0.75mg and 2.25 UPDRS points over 0.6mg pramipexole.
- Sequential correlations between changes from baseline will be 0.7 and 0.49 between these obtained at week 4 and at week 12.
- Missing observations rate of 10% occurring at random.
- The statistical model used in the simulation study was the Mixed Model for Repeated Measures (MMRM) (SAS® MIXED procedure with REPEATED sub-command) testing two contrasts: P2B001 0.6/0.75mg vs. rasagiline 0.75mg and P2B001 0.6/0.75mg vs. pramipexole 0.6mg at Week 12/Treatment Termination.
- In order to consider the study as successful both tested contrasts have to be statistically significant at 5% two-tailed each.

The simulation indicates that a total of 150 subjects per group treated with P2B001 0.6/0.75mg, rasagiline 0.75mg arm or pramipexole 0.6mg will provide 87.6% power to detect a statistically significant effect size favoring P2B001 0.6/0.75mg by 3 UPDRS points over rasagiline 0.75mg and 2.25 UPDRS points over pramipexole 0.6mg.

- To demonstrate the superiority of P2B001 0.6/0.75mg over pramipexole ER in the first secondary endpoint, namely, the change from baseline to Week 12/Treatment Termination in the ESS:
  - The power to meet this secondary endpoint was estimated using the two-sample t-test for mean difference at a two-sided alpha of 5% (SAS® POWER procedure).
  - The expected STD of the change from baseline was assumed to be 3.0 ESS points.
  - The expected treatment effect of P2B001 0.6/0.75mg over pramipexole ER is 1.5 ESS points.

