#### **15.6.10.4 Change from Baseline to Week 12/Treatment Termination in the Motor UPDRS (part III) Score**

The 4th secondary endpoint, namely, the change from baseline to Week 12/Treatment Termination in the motor UPDRS (part III) score will be considered as met if all of the 7 previous tested contrasts (primary endpoint, 1st, 2nd and 3rd secondary endpoints) as well the two contrasts: P2B001 0.6/0.75mg vs. pramipexole 0.6mg once daily and, P2B001 0.6/0.75mg vs. rasagiline 0.75mg once daily in the 4th secondary endpoint will all be met (total of 9 contrasts) at a two-tailed alpha level of 5% each.

The statistical model to be used for the analysis of the change from baseline to Week 12/Treatment Termination in the Motor UPDRS (part III) will be a Mixed Model for Repeated Measures (MMRM) (SAS® MIXED procedure with REPEATED sub-command). The model will include the following fixed effects: categorical week in trial by treatment interaction, CGR, and baseline Motor UPDRS (part III). The model will use the unstructured covariance structure and the REML estimation method and degrees of freedom will be adjusted using the Kenward-Roger method. Data from all three changes from baseline to post-baseline visits (weeks 5, 8 and 12) collected from all subjects randomized into the study will be used as response in the model.

The difference between P2B001 0.6/0.75mg to its 2 individual components at Week 12/Treatment Termination will be tested using 2 contrasts: P2B001 0.6/0.75mg vs. pramipexole 0.6mg and P2B001 0.6/0.75mg vs. rasagiline 0.75mg.

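### The primary and motor UPDRS models adjust for one pre-treatment score, although UPDRS part III is also rated at screening: a modest missed efficiency, not an error

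*Protocol*

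**What the plan says.** The primary model in Protocol 15.6.8, repeated in the Synopsis, is an MMRM on change in total UPDRS (parts II and III) with fixed effects "categorical week in trial by treatment interaction, country or geographical region (CGR), and baseline UPDRS score". The fourth key secondary, in 15.6.10.4, uses the same structure with baseline part III as its only score covariate. The change-to-last-observed-value (LOV) ANCOVA in 15.6.9.2 adjusts for treatment, region and baseline total UPDRS.

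Section 8.4.1 adds a second pre-treatment rating: "UPDRS part III will be completed also at screening visit to support diagnosis and the score will be included in the RAF". The RAF is the form on which the central eligibility committee approves a subject before randomization (16.4.2). The screening visit list (9.2.2) and Appendix I confirm the rating. Section 9.2.2 requires all screening results to be available before eligibility is decided, and 15.3 places randomization after screening. Part II is not rated at screening.

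None of the sensitivity analyses in 15.6.9 uses the screening score, and no reason is given for leaving it out. The SAP addendum deals with the mITT set and visit mapping and mentions no covariate.

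**The concern.** Part III makes up most of the primary score. Appendix IX has 27 part III ratings of 0 to 4, so 108 of the 160 points. A single rater-scored visit carries visit-to-visit noise, and a second reading of the same scale usually locates a subject better than one. Because the reading is taken before randomization, adding it to a linear model does not bias the treatment contrasts. It can lower their residual variance.

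What is at stake is power. Both primary contrasts must succeed, and every secondary test waits behind them (15.5). The 2.25-point contrast against pramipexole 0.6 mg carries nearly all the risk of failure. The protocol's only other response to a larger variance than planned is to enlarge the study by amendment (15.2).

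**Working it through.** **Inputs from Protocol 15.1.**
- Effects: "is 3 UPDRS points over rasagiline 0.75mg and 2.25 UPDRS points over 0.6mg pramipexole".
- SD: "The expected STD of the change from baseline was assumed to be 6.0 UPDRS points".
- Correlations: "Sequential correlations between changes from baseline will be 0.7 and 0.49 between these obtained at week 4 and at week 12". (The Synopsis and Appendix I put the first visit at week 5; this does not affect the arithmetic.)
- Missing data: "Missing observations rate of 10% occurring at random".
- Success rule: "both tested contrasts have to be statistically significant at 5% two-tailed each".
- 150 subjects per arm in the three main arms.

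**Step 1: reproduce the stated power.** The large-sample MMRM standard error of the week 12 contrast, with 10% missing independently at each visit, is 0.7132.
- Against rasagiline: 3/0.7132 − 1.960 = 2.246, power 98.8%.
- Against pramipexole 0.6 mg: 2.25/0.7132 − 1.960 = 1.195, power 88.4%.
- Both together (bivariate normal, correlation 0.5 from the shared P2B001 arm): 87.8%.

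Monotone dropout gives 87.1%, and missingness at week 12 only gives 87.9%. The stated 87.6% is reproduced without the screening score.

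**Step 2: model the second reading.** The documents give no UPDRS measurement error, so these values are assumed: true part III SD (s3) 6 to 10, true part II SD (s2) 3 to 4, correlation between them (c) 0.4 to 0.6, visit error SD 2 to 3.5 for part III (e3) and 1 to 1.5 for part II (e2), and no drift between screening and baseline. Then:
- Error variance of the total: Ve = e3² + e2².
- Variance of baseline total: VB = s3² + s2² + 2·c·s3·s2 + Ve.
- Variance of screening part III: VS = s3² + e3².
- Covariance of the two: K = s3² + c·s3·s2.
- Variance of change explained by baseline alone: r1 = Ve²/VB.
- Explained by baseline plus screening: r2 = Ve²·VS/(VB·VS − K²).

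Middle case (s3 = 6, s2 = 3, c = 0.4, e3 = 3, e2 = 1): Ve = 10, VB = 69.4, VS = 45, K = 43.2. So r1 = 100/69.4 = 1.441 and r2 = 4500/(3123 − 1866.24) = 3.581. Residual variance falls from 36 − 1.441 = 34.56 to 36 − 3.581 = 32.42, a cut of 6.2%. With 10% missing observations allowed for, the variance of the week 12 contrast falls by 5.9%.

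**Step 3: joint power over the 96 combinations.** The 6.0 can be the raw SD of change or the SD already adjusted for baseline. Both readings are shown, for the combinations with the smallest, middle and largest cut.

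| Case | Cut in contrast variance (6.0 raw) | Joint power, 6.0 raw | Joint power, 6.0 adjusted |
|---|---|---|---|
| Low | 1.9% | 88.13% to 88.75% (+0.6) | 87.83% to 88.46% (+0.6) |
| Middle | 5.9% | 89.10% to 90.92% (+1.8) | 87.83% to 89.71% (+1.9) |
| High | 12.7% | 89.00% to 92.81% (+3.8) | 87.83% to 91.77% (+3.9) |

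On the adjusted reading the cuts are 1.9% to 12.3%, equal to about 3 to 18 subjects per arm (150 × 0.0187 and 150 × 0.1227).

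**Step 4: let correlation decay.** Take a raw change SD of 6.0 and an assumed baseline SD of 10. Then 36 = 2·100·(1 − ρ), so the baseline to week 12 correlation is 0.82 and the residual share given baseline is 1 − 0.82² = 0.328. Even for a full total-score screening reading, the further cut is (r_sw − 0.82·r_sb)²/[(1 − r_sb²)·0.328], where r_sb is the screening-baseline correlation and r_sw the screening-week 12 correlation. With r_sb of 0.88 to 0.92 it is 0 to 2% when r_sw is 0.73 to 0.76, and 1% to 5% when r_sw is 0.78. It reaches 10.6% only at 0.88 and 0.81. It vanishes when r_sw equals 0.82·r_sb.

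**The case against.** The strongest reply is that nothing here is wrong. Adjusting a change score for its own baseline is standard and valid. The power claim stands without the screening score, and no alpha level or decision rule depends on it. All of that is right.

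A reader might infer a much larger gain. Under compound symmetry, two full total-score readings with ρ = 0.82 would cut residual variance from 0.328 to 1 − 2·0.82²/1.82 = 0.261, about 20%. The plan does not support that. Compound symmetry of raw scores makes every pair of changes from baseline correlate 0.5, whereas 15.1 assumes 0.7 between adjacent visits and 0.49 from first to last, which is decay. Screening also covers part III only. Nor may the two readings of 6.0 be mixed: if the adjusted SD were, for illustration, 5.50, joint power before any change would already be 92.9%, and the room for improvement would be smaller.

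Three practical objections stand in part. Screen failures may rescreen and the interval to baseline may reach 90 days (9.2.2), so the score needs a definition and its age will vary. Completeness is likely but not certain: the SAP addendum reports one subject without even a baseline UPDRS. The eligibility criteria set no UPDRS cut-off, but the score does go to the committee that accepts or rejects subjects, so freedom from rating pressure is an inference. These points shrink or complicate the gain; they do not bias the linear-model contrasts.

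**Conclusion.** The concern holds as a missed efficiency in the protocol's primary and motor UPDRS models. The expected cut in contrast variance is roughly 2% to 12%, median about 6%, or about 0.6 to 4 points of joint power and typically about 2. These figures rest on assumed score and error SDs and on no drift between screening and baseline. Rapid decay takes the gain close to zero. The motor endpoint was not quantified separately.

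A reader might infer that the primary analysis is flawed or the trial underpowered for want of this covariate. The documents do not support that, since the 87.6% reproduces as planned. Nor do they establish that the final analysis omits the score. Under 15.13 the SAP overrides the protocol, and only its addendum was supplied. That addendum shows SAP version 2.0 departing from the protocol elsewhere, making mITT the principal efficacy set where Protocol 15.4 names ITT. The finding therefore applies to the protocol text.

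**What to change.** First check the covariate list in the body of SAP version 2.0. If the screening score is absent, then before unblinding:

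- Add screening UPDRS part III as a continuous covariate, alongside the baseline score, in the primary MMRM (15.6.8), the motor UPDRS MMRM (15.6.10.4) and the LOV ANCOVA (15.6.9.2).
- Define it as the last part III score recorded at screening before randomization, so that rescreened subjects are covered, and state a simple rule for any missing value.
- Leave the logistic responder model (15.6.9.3) unchanged. A further prognostic covariate there would change the conditional odds ratio being estimated, so it would not be a pure gain in precision.

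The cost is SAP wording and about one model degree of freedom, with no new visit or assessment.
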